identify the model that best characterizes patterns of growth. We can also specify an additional nonlinear quadratic factor, a higher order polynomial function to capture any nonlinearity. Accelerated or decelerated change would be specified with loadings fixed at 0, 1, 4, and 16. A sequential set of models tests the latent variances and model fit across a random intercept, linear growth, and quadratic model to determine the optimal growth pattern. The comparative effectiveness hypothesis for observed parenting is shown in Figure 2 as linear growth. Group Based and Web Facilitated will be contrasted to the Self-Directed omitted group. Analyses will test that the Group Based effect ($\beta_1 > 0$) and the Web Facilitated ($\beta_2 > 0$) will show greater 2-year improvements relative to Self-Directed. For the LGM in Figure 2 we estimated power using Mplus Monte Carlo simulations with 1000 replications. An advantage of this approach is the ability to incorporate specific patterns of expected attrition over time. For the figure in Figure 3, contrasts for Group Based and Web Facilitated were fixed at a mean of .33 and variance of .22 representing the random allocation across groups. The latent initial status intercept and latent growth factors were specified reflecting a commonly observed ratio of 5:1 for the variance components (Initial Status $\psi_2 = .5$ and SD = .70; and Linear Growth $\psi_2 = .1$, SD = .31). The effect size (ES) is then the ratio of group contrast mean differences in the latent growth factor divided by the SD for growth. A sample size of 306 (cumulative attrition of 15% over 2 years, specified as .05, .10 and .15 over time) obtained power of .98 respectively to detect small effects (ES=.10) for β_1 and β_2 relative to Self-Directed and likewise for child, couple, parent adjustment.

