ADAPT Self Directed Web. In the self-directed web-only ADAPT condition, participants have access to the full ADAPT website (10 modules, online discussion forum) but do not have access to a 'live' in-person facilitator. Participants are directed to the first ADAPT session, and as each session is completed (all materials in a session opened by at least one parent) families receive a personalized congratulations email and thank you gift card with directions to continue to the next module. Participants may see the entire program on the ADAPT dashboard; they are encouraged to proceed in the specified order. Each online session consists of a skills video (demonstrating a specific skill), a practice video (modeling how parents practice skills with child(ren)), downloadable summaries of key skills, fillable PDF forms with home practice assignments, a knowledge quiz, and downloadable mindfulness exercises that can be played directly from the ADAPT site as well as from smartphones, tablets, and computers.

ADAPT individualized web-facilitated. This condition comprises access to the full ADAPT web program as described above, with augmentation of individual facilitator web support (i.e. the facilitator connects via Google Hangout). Facilitators meet with families at a mutually convenient time weekly (10-14 weeks, approximately 3 sessions per month). Sessions cover the same topics as in the group condition, but the material is tailored for families and sessions are shorter (1 hr vs 2 hrs) to reflect the pace of teaching skills to individual families

PROTOCOL TITLE: Comparing Web, Group, and Telehealth Formats of a Military

Parenting Program

VERSION DATE: May 4, 2018

vs. groups. The web program is used as a springboard for each individual session and as a reference for home practice assignments. For example, in session 2, ‘Giving Effective Directions’, the facilitator introduces the family to effective and ineffective directions via role play (as in ADAPT groups), refers the family to the online skill video, and provides live (Hangout) role play practice with parents. The facilitator explains and shows parents the online home practice assignment. Facilitators will offer referrals for other services (e.g. individual therapy for PTSD) to VA and other community mental health providers, as needed.

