assessments with the target 5-12 year old child, and complete parent-child observational tasks, and adult measures (approximately 100 minutes total). Families who prefer assessment outside the home may go to the local UMN or UM project office.

Note: Child care is offered to families for the siblings that are not participating in the research. In the event that child care staff are not available we will offer families a \$30 gift card stipend to provide their own child care during the in-home assessment.

5. Teachers will be contacted (at each time point) via secure, encrypted email, with an explanation of the study, and a copy of the parent's release of information. They will be directed to the study website to complete questionnaires. Teachers not responding will receive materials by mail, with follow-up calls. Teachers who do not want their compensation may choose to give the gift card back to ADAPT or to MCEC.

6. Following BL assessment, participants are electronically given random assignment to the G, W, or F study conditions, with 120 families assigned to each condition. The group condition will be run in three cohorts, with 2 groups of up to 10 families in each cohort of 20 families (up to 60 families in each of the two sites – i.e. 120 total, considerably more than we estimate will participate). In both online conditions, families may participate as they enter the study. However, given the necessity of running groups in cohorts and the need for equivalence in analysis, we will also assign individuals in the web conditions to a cohort.

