PROTOCOL TITLE: Comparing Web, Group, and Telehealth Formats of a Military Parenting Program

VERSION DATE: May 4, 2018

be completed during the baseline or follow-up, or study staff will provide funds for the family to travel to a local library, University, etc. to gain computer access.

Sources of Materials

- Research material obtained from human subjects will consist of data collected specifically for this study.

The data will include:

1. Web-based questionnaires filled out by families
2. Observational coding data based on videotaped parent-child interaction tasks completed by families
3. Short questionnaire packets filled out by families and teachers
4. Short surveys and web conference calls completed by expert panel members.
5. Audio and video tape of parent's response to KidVid (video of parenting tasks)

Measures and Assessments:

There are 4 assessments: Time 1- baseline (BL, prior to start of the intervention), Time 2 - six months post BL (post-intervention, given 4-5 month intervention at 3 sessions/month, allowing for holidays, etc), Time 3- 12 months following BL, and Time 4, 24 months after BL. Assessments are weighted to be gathered in the first year, (BL, 6, and 12 months) to gauge intervention effects immediately at posttest (i.e., T2) and at T3, which is when parenting and teacher report outcomes indicated change in prior studies. All measures (i.e., child, parent, and teacher report, and direct observations) will be gathered annually (T1, T3, T4), ensuring that teachers are different at each assessment. At T2, only parent report data will be gathered, online, (no in-home assessment) to minimize participant burden in Year 1, and because in prior studies observed parenting and teacher report outcomes indicated change at 12 months, while parent report indicated some change immediately posttest. Child self-report measures will be gathered (and were standardized with) children over age 8. Measures are summarized below:

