12.0 Recruitment Methods

12.1 Recruitment Process:

Recruitment flyers promoting the study will be distributed to our partners (NG, VA, M-SPAN). In addition, the PI has been invited by the MN ARNG to present at reintegration workshops which are mandatory for all soldiers returning from OEF/OIF deployment, and flyers will be handed out there. Flyers provide the phone and email contact information for the researchers, and the study site URL. The website guides parents to a brief explanation of the project, and a description of project confidentiality and its limits. Refer a friend post cards will be distributed to previous ADAPT study participants and current participants (as recruitment occurs). A recruitment/outreach booth will be set-up at the MN State Fair on Military Appreciation Day.

Interested participants will be directed to an anonymous online screening instrument. This screen determines eligibility based on the above stated inclusion and exclusion criteria. Eligible participants will next complete a brief contact information form, followed by an online informed consent that will provide information about study risks, benefits and about the possibility of being randomly assigned to either an intervention (E) group or SAU comparison group. In reintegrating families with two at-home participating parents/caregivers, each will complete a separate informed consent.

PROTOCOL TITLE: Comparing Web, Group, and Telehealth Formats of a Military Parenting Program

VERSION DATE: May 4, 2018

Eligible participants will next complete a brief contact information form, followed by an online informed consent providing information about study risks, benefits and the possibility of being randomly assigned to one of three intervention conditions: group-based ADAPT (G), web-only/self-directed ADAPT (W), or individualized web-facilitated ADAPT (F). In reintegrating families with two at-home participating parents/caregivers, each will complete a separate informed consent.

Consenting participants will be provided a contact number to speak to the PI or study coordinator with questions. Families requesting a telephone screening will be asked for verbal consent for the team to maintain contact through reminder emails and phone calls as needed to complete informed consent and BL online assessments. Informed consent may also be completed at the in-home assessment.

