- Interested participants will be directed to an anonymous online screening instrument. This screen determines eligibility based on the inclusion criteria mentioned above. To be eligible for the study, families must agree to random assignment to experimental or control conditions, be willing and able to complete assessment and intervention, and live within the catchment area. See Inclusion/Exclusion Criteria for eligibility guidelines.

- Eligible adult family participants will next complete a brief contact information form, followed by an online informed consent that will provide information about study risks, benefits and about the possibility of being randomly assigned to one of the three conditions. Families will be assured that no services or relationship

PROTOCOL TITLE: Comparing Web, Group, and Telehealth Formats of a Military Parenting Program

VERSION DATE: May 4, 2018

with the NG or the University of Minnesota or University of Michigan will change or be adversely affected regardless of whether or not they choose to participate in the study.

- The voluntary nature of participation and the ability to withdraw from the project at any time without penalty will be emphasized. In reintegrating families with two at-home participating parents/caregivers, each will complete a separate informed consent.
- Consenting adult family participants will be provided a contact number in order to speak to the PI or study coordinator with any questions. Families who request a telephone screening (e.g., families whose internet is not accessible at the time of the call) will be asked for verbal consent for the research team to maintain contact through weekly reminder emails and phone calls as needed to complete informed consent and baseline (BL) online assessments. Where informed consent is not completed prior to the home visit, it may be completed at the beginning of the in-home assessment.

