The anticipated potential adversity inherent in assessment is limited to those situations described above and is addressed by the timely intervention of a licensed clinical psychologist skilled in risk assessment and mandatory reporting requirements.

We have never had a staff safety issue while in a subject's home and have done more than 500 in-home assessments to date. In our assessment tech training, our techs are given a manual with instructions for dealing with different situations, and we do discuss this issue so all of our techs know what to do in case of an emergency.

As a part of the ongoing statistical analyses conducted to evaluate the effectiveness of the prevention trial, the experimental and control groups will be routinely compared on several dimensions, including the occurrence of the type of adverse events described above. With any significant group difference, the relevant covariates will be thoroughly examined in order to understand more completely the relationship between the variables of interest and potential effects of the intervention. The results of our analyses, including the occurrence of adverse events, will be reported both to our IRB and to NIDA through annual progress reports. We will also report adverse events to others, as directed by our IRB or NIDA Program Official.

Reporting Procedure for Serious Unanticipated Adverse Events

In the event of an unanticipated serious adverse event, the project PI will ensure that these events are reported to the NIDA Program Official within 24 hours by phone, fax, and/or email and will submit a written report to the Program Official no more than two days later. The project staff will also utilize the following reporting procedures:

1. When the grant staff and/or PI become aware of a serious adverse event, reporting requirements must be implemented in a timely manner.

PROTOCOL TITLE: Comparing Web, Group, and Telehealth Formats of a Military

Parenting Program

VERSION DATE: May 4, 2018

2. PI completes a University of Minnesota "Adverse Event Reporting Form" and submits the form to the Human Subjects Officer at the U of Minnesota.
3. The Human Subjects officer immediately distributes the form to the following individuals or groups as required: Center Administrator, Center Management Committee, and Center IRB Officials.

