
19.0 Provisions to Monitor the Data to Ensure the Safety of Participants – NA

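### Section 14.1 plans an experimental-versus-control comparison of adverse events in a trial of three active arms, and for events that can surface in facilitator contact that comparison cannot separate detection from harm

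*Protocol*

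**What the plan says.** Protocol section 14.1 (Foreseeable Risks) states that "the experimental and control groups will be routinely compared on several dimensions, including the occurrence of the type of adverse events described above". If a significant difference appears, relevant covariates are to be examined to understand possible intervention effects. The results go to the IRB and to NIDA in annual progress reports.

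The design is different. Under section 5.2, item 6, "participants are electronically given random assignment to the G, W, or F study conditions, with 120 families assigned to each condition", and sections 1.1 and 4.1 describe all three conditions as forms of ADAPT. Two-arm wording also survives elsewhere. Sections 12.1 and 23.3 speak of being "randomly assigned to either an intervention (E) group or SAU comparison group", and section 14.1 says that "families must agree to random assignment to experimental or control conditions".

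Live contact with staff depends on the arm. G has 14 sessions of 120 minutes (sections 3.1 and 4.1), in groups of five to ten families (section 5.2, item 7). F has weekly one-hour sessions over 10 to 14 weeks (section 4.1). Self-Directed families do not "have access to a 'live' in-person facilitator" (section 4.1). Home assessments take place at T1, T3 and T4 in every arm, and T2 is an online parent survey without a home visit (section 5.2, Measures and Assessments).

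**The concern.** There are two linked problems. First, the labels experimental and control belong to no named arm, so the comparison cannot be run as written without a guess.

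Second, some of the events concerned become known when staff see or hear something. Section 14.1 covers disclosure of child abuse or of threat to self or others. In G and F the facilitator explains the reporting limits during orientation (section 5.2, items 7 and 9) and then meets the family repeatedly. Section 18.1 has project staff trained to recognise and report suspected abuse, neglect or endangerment. W has no matching sessions. With equal true rates, the arms with sessions could record more such events simply because someone was there to notice.

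At stake is how the annual safety reports are read, and whether any later statement that self-directed web delivery is as safe as facilitated delivery could be supported.

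**Working it through.** **Which arms could be meant.** Section 22.1 speaks of an added consent for the experimental condition and mentions only in-person groups and web-facilitated families. Section 1.1 says that "Group Based and Web Facilitated will be contrasted to the Self-Directed omitted group". Together these suggest G and F against W, 240 families against 120. This is an inference: section 5.2, item 8, also gives W families a consent form for the program, and no section calls W a control.

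**Scheduled contact.** The protocol states no contact ratio, so there is no figure to reproduce. Assumptions: full attendance, one F session per stated week, and the 100 minutes given for the baseline home visit applied also at T3 and T4.

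- Sessions: G 14 × 2 h = 28 h; F 10 to 14 × 1 h = 10 to 14 h; W 0 h.
- Home visits after randomisation (T3, T4): 2 × 100 min = 3.33 h in each arm.
- G to W: (28 + 3.33)/3.33 = 9.4. F to W: (10 + 3.33)/3.33 = 4.0 to (14 + 3.33)/3.33 = 5.2.
- Counting the pre-randomisation baseline visit as well (5 h): G to W 33/5 = 6.6; F to W 15/5 = 3.0 to 19/5 = 3.8.

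Sensitivity of the G to W ratio on the 5 h base:

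- Assumed 75% attendance: (21 + 5)/5 = 5.2.
- Assumed 50% attendance: (14 + 5)/5 = 3.8.
- Group time divided among 5 families: (5.6 + 5)/5 = 2.1.
- Group time divided among 10 families: (2.8 + 5)/5 = 1.6.
- Events that can arise only at assessments: 5/5 = 1.0.

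These are ratios of scheduled time, not of detection.

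**What unequal detection could do (all rates assumed).** Let the true proportion of families with an event, p, be the same in every arm. Let 30% of events be found through assessments, and let facilitators in G and F independently find a share f. The detected proportion is p × [1 − 0.7 × (1 − f)] in G and F, and 0.30p in W.

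- f = 0.5: 0.65p against 0.30p, reported risk ratio 2.17.
- f = 0.3: 0.51p against 0.30p, reported risk ratio 1.70.

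The chance that a two-sided Fisher test at .05 (240 against 120) rejects, summed exactly over the two binomial distributions, is:

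| True p | f = 0.5 | f = 0.3 |
|---|---|---|
| 2% | 0.5% | 0.5% |
| 3% | 1.9% | 1.0% |
| 5% | 8% | 3% |
| 10% | 23% | 10% |
| 15% | 37% | 16% |

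The distorted ratio does not depend on p. The false-rejection rate does, and it exceeds 5% only when such events are fairly common.

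**Why covariates do not help.** Facilitator time is set by the arm and is zero throughout W. Attendance varies within G and F, but it arises after randomisation and has no counterpart in W. Adjustment cannot recover what would have been noticed in W.

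**The case against.** The strongest reply concerns scope. Section 14.1 ties the anticipated adversity to assessment, and the numbered risks #1 to #5 are mostly assessment discomfort, confidentiality and misunderstanding of data use. These arise from procedures scheduled alike in all arms. That stands, and it confines the point to disclosures, threats and distress that can also surface in sessions.

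Other routes are open to every arm. The consent statement in section 18.1 invites any participant in serious difficulty to contact staff, reporting limits are explained to everyone (section 14.1), and the measures table has parents complete the CES-D, AUDIT and PTSD checklists online at T2. That stands too: a W family is not invisible between home visits.

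A reader might infer that the comparison would show detection instead of harm, or that W is bound to look safest. The protocol supports neither, since it gives no event or detection rates. A reader might also take 6.6 as a detection ratio. It is maximum scheduled contact, includes a visit before randomisation, and credits each family with all the shared group time.

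Finally, section 19.0 reads "Provisions to Monitor the Data to Ensure the Safety of Participants – NA", which could suggest that adverse events go unhandled. They do not: section 14.1 sets annual reporting, 24-hour notice of unanticipated serious events and an expedited IRB meeting. Nor does it prescribe a conclusion of harm when groups differ.

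None of this supplies the missing arm names or makes detection equal for the affected events.

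**Conclusion.** The point holds in a limited form. The safety comparison names groups that the design does not have. Its most workable reading, G and F against W, sets arms with facilitator sessions against an arm without them. For events that can surface in those sessions, a raw between-arm difference mixes detection with harm, and the planned look at covariates cannot pull them apart. Events arising only from assessment are not affected.

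The imbalance in scheduled session time is certain: up to 28 h (shared), 10 to 14 h and 0 h at full attendance. Its effect on reported events is not known. The risk ratios of 1.7 to 2.2 and the rejection rates above illustrate assumed values only, and at a true rate of 3% or less the test would not reject more often than its nominal level. The unclear labels are part of a wider wording fault, since two-arm phrases also appear in sections 12.1 and 23.3.

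**What to change.** In section 14.1:

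1. Replace the experimental and control labels with the three randomised arms, G, F and W.
2. Record for each event how it was first found: online survey, home assessment, participant-initiated contact or facilitator session.
3. Base the formal between-arm comparison on events after randomisation found through sources common to all arms: the T2 online survey and the T3 and T4 assessments. Show participant-initiated contact as its own source. Leave out events found at T1, which precedes randomisation.
4. Report events first found in facilitator sessions separately by arm, descriptively, so that harm connected with the sessions stays visible.

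Two additions are optional: an identical adverse-event question in each online survey, and a cross-reference from section 19.0. The two-arm phrases in sections 12.1, 14.1 and 23.3 can be corrected in the same amendment.

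The cost is protocol wording, one recorded field per event and an extra table. The downside is that fewer events enter the formal comparison, so it will be less able to detect a true difference.

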14.2 Reproduction Risks: NA

14.3 Risks to Others: NA

15.0 Incomplete Disclosure or Deception

15.1 Incomplete Disclosure or Deception: NA

16.0 Potential Benefits to Participants

16.1 Potential Benefits:

Families will benefit from receiving prevention services from well-trained and well-supported group facilitators. Families will have increased possibility of experiencing significant improvements in their child's adjustment as well as delay and prevention of substance use and abuse. Families will be compensated for their participation in assessments. The web-enhancement will give families access to an online training platform which allows already overburdened parents to balance the demands of work and family with their commitment to improving their parenting skills and fostering optimal development for their children.

Additionally, participating in a parenting program designed specifically for the families of reintegrating military personnel will reduce the psychological barriers to help-seeking for this high-risk population. In light of the considerable personal and public costs associated with compromised parenting, the potential benefits of participating in this study greatly exceed the potential risks.

